12.2.1 Three-month Follow-up

Participant reported outcomes will be assessed:

- NRS to assess phantom limb pain and chronic stump pain
- Health-related QoL, measured by EQ-5D-5L (59)
- Hospital Anxiety and Depression Scale (HADS) (60)
- Healthcare resource use questionnaire (including subsequent amputations and hospital readmissions, drug administration, number of physiotherapy or occupational therapy consultations and additional procedures performed)
- Prosthesis fitting rate (using a prosthesis for standing, transferring, or walking; SIGAM 'B' or greater), and (if applicable) time to achieve prosthesis fitting and level of independence assessed by SIGAM (63)

12.2.2 Six-month Follow-up

At the 6 month follow up, all the PROs will be collected as per the 3 month follow up, and a medical note review will collect:

• Mortality, including cause of mortality

- Delayed wound healing of the surgical wound (defined as absence of complete epithelialisation of the wound)
- Residual limb surgery (revision or debridement)
- (For unilateral amputees) MLLA of contralateral limb
- Length of hospital stay (censored at 6 months in the unlikely event that the participant remains in hospital at 6-month follow-up), including re-admissions after discharge, used to calculate DAOH-90 and time spent in level 2 or 3 care.

12.2.3 Longer-term Follow-up

Participants will be asked to consent to routine data-linked longer-term follow-up. Should our results indicate longer-term follow-up is desirable (for example, to further explore the impact of PNC usage on chronic pain), we will apply for further funding for this.

12.3 Qualitative Process Evaluation

Although a small-scale process evaluation was conducted as part of the PLACEMENT feasibility trial, Medical Research Council guidance recommends that this should be repeated at full trial stage, as new issues are likely to be identified when testing the intervention in a larger and more diverse group of participants (64). A qualitative process evaluation can help interpret trial findings and aid the implementation of successful interventions in practice (65). Therefore, we will conduct a qualitative evaluation of PNC implementation, comprising semi-structured interviews with approximately 20 to 30 trial participants and/or relatives/carers and approximately 10 to 20 HCPs across different sites (around three to six sites, total: 30 to 50 interviews). Trial participants and HCPs will be sampled purposively to encourage diversity.

More specifically this qualitative evaluation will aim:

 to explore how delivery of the intervention was achieved and what was delivered (qualitative measure of fidelity); how the intervention components and delivery processes worked in the real healthcare setting (covering feasibility, implementation, practicality of intervention), and acceptability of the trial to participants and intervention deliverers (e.g. how did the consent models work, how was randomisation understood, was trial information understood, to what extent was there equipoise amongst stakeholders).

• To explore the experiences and understanding of participants in the PLACEMENT trial about the participant's condition and MLLA (where appropriate), and experience of decisions around care and participation in the trial.

12.3.1 Semi-structured Interviews

We will use semi-structured qualitative interviews to encourage participants to initiate and elaborate on topics most important to them which we may not have pre-empted if using survey type closed questions. Semi-structured interviews will be conducted with HCPs and trial participants. Interviews may be undertaken remotely (via telephone or teleconference) or in-person. The length of the interviews will vary, but we expect them to take about 30 to 60 minutes. Brief demographic details will be taken by the interviewer (interviewee age, gender etc.) and used to describe the interviewee sample. Field notes may be made by the interviewer following the interview which will include reflections on the interview process, overall observations, and any relevant contextual details.

Trial Participant Interviews

Interviews with participants will explore understanding of the trial (e.g., the randomisation process). They will also explore experiences and acceptability of the PNC, experiences of undertaking follow-up, and further explore/develop themes identified in the feasibility trial and in our focus group, including rehabilitation experiences, information needs following MLLA, and participant anxieties and satisfaction related to pain management. For example, we found considerable uncertainty amongst participants regarding the rehabilitation process, unrealistic expectations regarding future mobility and anxiety associated with patient-controlled analgesia. As these are issues identified in our previous research as important to patients, gathering more robust data will lead to recommendations for changes to patient care which have the potential to impact on QoL.

Healthcare Professional Interviews

Interviews with HCPs will explore how the intervention was delivered, how the intervention and components worked in a real healthcare setting, acceptability of the intervention, decision making around care of patients, and views on the trial processes. Findings from early HCP and participant interviews (specifically regarding understanding of the trial, the randomisation process and follow-up) will be fed back to the TMG during the trial pilot phase. Separate consent to contact forms will be used to identify healthcare professionals from the clinical care team. Completed consent to contact forms

will be sent from the site to the research team. The research team will contact 10 to 20 of HCPs and go through a separate information sheet with them before obtaining their verbal consent to proceed with the interview. Written copies of this information sheet will be available at sites for HCPs to read after filling in a consent to contact form.

Topic Guide

The semi-structured interview topic guide will be developed from a review of previous research with input from the multi-disciplinary research team to avoid bias in wording of questions. The topic guide will be refined, as necessary. The direction of questions may be led by the participants themselves and therefore the interview topic guide will remain flexible, in keeping with the method of semi-structured interviewing. Interviews will be recorded and transcribed verbatim. Transcripts to be used for analysis will be de-identified with personal details such as name, address, and date of birth removed.

12.3.2 Sample Size

A purposive sample of HCPs who are involved in delivering the PLACEMENT Trial will be identified from the sites. The sample strategy will be developed to address representation from around three to six different sites and encourage variation in HCP role (e.g., ward nurse, consultant, research nurse etc.) We anticipate that interviews with around 10 to 20 professionals based on saturation and breadth of views expressed should be sufficient.

A purposive sample of PLACEMENT trial participants will be identified. We anticipate that a sample size of around 20 to 30 participants will be sufficient. The sample strategy will be developed to include participants from both the intervention and control arm, and inclusion of different sites. By sampling along these lines, we envisage there will be a range in terms of age, gender, ethnicity, and level of amputation to encourage maximum variation.

With regards to the sample size for both HCPs and trial participants, the qualitative researcher(s) will make pragmatic decisions along with the research team regarding when enough is known about certain themes (i.e., data saturation has occurred).

13 Pharmacovigilance

The PI is responsible for ensuring that all site staff involved in this trial are familiar with the content of this section.

All SAEs must be reported immediately (and within 24 hours of knowledge of the event) by the PI at the participating site to the CTR PV and Safety Specialist unless the SAE is specified as not requiring immediate reporting (see Section 13.2). This includes SAEs related to IMPs.

13.1 Definitions

Term	Definition
Adverse Event (AE)	Any untoward medical occurrence in a participant or clinical trial participant administered a medicinal product and which are not necessarily caused by or related to that product
Adverse Reaction (AR)	Any untoward and unintended response in a clinical trial participant to an investigational medicinal product which is related to any dose administered to that participant
Serious Adverse Event (SAE)	 Any adverse event that - Results in death Is life-threatening* Required hospitalisation or prolongation of existing hospitalisation** Results in persistent or significant disability or incapacity Consists of a congenital anomaly or birth defect Other medically important condition***
Serious Adverse Reactions (SARs)	Any SAE occurring in a clinical trial participant for which there is a reasonable possibility that it is related to the IMP at any dose administered.
Suspected Unexpected Serious Adverse Reactions (SUSARs)	A SAR, the nature and severity of which is not consistent with the Reference Safety Information (RSI) for the IMP. the definition of serious refers to an event in which the trial participant was at risk of

Table 3 Definitions of Adverse and Serious Adverse Events and Reactions

***Note:** The term 'life-threatening' in the definition of serious refers to an event in which the trial participant was at risk of death at the time of the event, or it is suspected that used or continued used of the product would result in the subject's death; it does not refer to an event which hypothetically might have caused death if it were more severe.

**** Note:** Hospitalisation is defined as an inpatient admission, regardless of the length of stay, even if the hospitalisation is a precautionary measure for continued observation. Pre-planned hospitalisation e.g., for pre-existing conditions which have not worsened, or elective procedures, does not constitute an SAE.

******* Note: other events that may not result in death, are not life-threatening, or do not require hospitalisation, may be considered as an SAE when, based upon appropriate medical judgement, the event may jeopardise the participant and may require medical or surgical intervention to prevent one of the outcomes listed above.

13.2 Trial Specific SAE Reporting requirements

In addition to the SAE reporting requirements defined in Table 3, for the purposes of this trial the following events will also be considered SAEs and must be captured on the SAE form and reported to the CTR with 24 hours of knowledge of the event:

- Infection around PNC exit site
- Local anaesthetic toxicity reactions (see Section 11.6)

For the purposes of this trial the following events will **not** require reporting as SAEs:

• AEs as a result of surgical complications of CTCAE grades 1 and 2 as listed in the protocol (Table 6, page 64 - 65)

These should be completed in the participant's notes and on the relevant CRF page and forwarded

to the CTR in the normal timeframes for CRFs.

Pre-existing conditions should only be reported if they met the definitions for an SAE and if the condition worsens by at least one CTCAE grade.

13.3 Causality

Causal relationship will be assessed for IMPs and procedures:

Table 4 IMP

IMP: Levobupivacaine hydrochloride, Ropivacaine hydrochloride, Bupivacaine hydrochloride

Procedure: Placement of perineural catheter during MLLA

The PI (or another delegated medically qualified doctor from the trial team) and CI (or another medically qualified doctor from the Trial Management Group) will assess each SAE to determine the causal relationship:

Table 5 Definition of Relationship with IMP

Rela	ationship	Description	Reasonable	possibility
			that the SAE	may have
			been caused b	y the IMP?

Unrelated	There is no evidence of any causal relationship with the trial/intervention	No
Unlikely	There is little evidence to suggest there is a causal relationship with the trial/intervention (e.g., the event did not occur within a reasonable time after administration of the trial medication). There is another reasonable explanation for the event (e.g., the participant's clinical condition, other concomitant treatment).	No
Possible	There is some evidence to suggest a causal relationship with the trial/intervention (e.g., because the event occurs within a reasonable time after administration of the trial medication). However, the influence of other factors may have contributed to the event (e.g., the participant's clinical condition, other concomitant treatments).	Yes
Probable	There is evidence to suggest a causal relationship and the influence of other factors is unlikely.	Yes
Definite	There is clear evidence to suggest a causal relationship and other possible contributing factors can be ruled out.	Yes

The causality assessment given by the PI (or delegate) cannot be downgraded by the CI (or delegate), and in the case of disagreement both opinions will be provided.

13.4 Expectedness

The CI (or another delegated appropriately qualified individual) will assess each SAR to perform the assessment of expectedness.

The expectedness assessment should be made with reference to the current Reference Safety Information (RSI) for each IMP. Expectedness decisions must be based purely on whether the event is listed in the RSI; other factors such as the participant population and participant history should not be taken into account. Expectedness is not related to what is an anticipated event within a particular disease. SARs which add significant information on specificity or severity of a known, already documented adverse event constitute unexpected events. Fatal and life-threatening SARs should not be considered expected (unless explicitly stated in the RSI and approved by the NCA). For example, an event more specific or more severe than that described in the RSI is considered unexpected.

The table below lists the expected events in relation to surgery and this should be used as the RSI when assessing the expectedness of AEs causally related to surgery. Anticipated treatment related AEs of grade ≤ 2 are not subject to expedited reporting. These should be completed in the participant's notes and on the relevant toxicities CRF (if applicable) and submitted to the CTR in the normal timeframes for CRFs.

Blood and lymphatic system disorders	Renal and urinary disorders	Nervous system disorders
 Anaemia Postoperative hemorrhage Hematoma 	 Acute kidney injury Haematuria Urinary retention 	 Dizziness Dysarthria Headache Paraestheis Presyncope Seizure/convulsions Spasticity Stroke Transient ischemic attacks (TIAs) Tremor Phantom pain
Ear and labyrinth disorders Tinnitus 	 Immune system disorders Allergic reaction (If related to infusion, use 'Infusion related reaction' - do not report both) 	Psychiatric disorders • Agitation • Anxiety • Confusion • Delirium • Delusions • Hallucinations • Psychosis
Cardiac disorders Chest pain – cardiac (includes angina) Sinus bradycardia Sinus tachycardia Heart failure Myocardial infarction	 Infections and infestations Phlebitis infective Urinary tract infection (UTI) Wound infection Enterocolitis infectious (includes clostridium difficile) 	 Respiratory, thoracic and mediastinal disorders Atelectasis Dysponea Pleural effusion Lung infection (including pneumonia)

Table 6 Expected Events in Relation to MLLA (CTCAE v5.0)

 Gastrointestinal disorders Constipation Ileus Bowel obstruction Diarrhea Nausea Vomiting 	 Injury, poisoning and procedural complications Fall Fracture Infusion site extravasation Infusion related reaction Wound dehiscence 	 Surgical Need for revision amputation Retained foreign body (including unable to remove PNC)
General disorders	 Eye disorders Visual disturbances (includes blurred vision, flashing lights) 	Musculoskeletal Back pain
Metabolism and nutrition disorders • Acidosis • Dehydration	 Skin and subcutaneous tissue disorders Skin ulceration (includes pressure ulcers) 	 Vascular disorders Hypertension Hypotension Thromboembolic event Phlebitis

The table below lists the RSI's that should be referenced:

Table 7 Reference Safety Information

IMP	RSI to be used for expectedness assessment	Relevant section to be used for expectedness assessment
Levobupivacaine	SmPC for Levobupivacaine 0.125% w/v Solution for Infusion	Section 4.8 of SmPC
Ropivacaine hydrochloride	SmPC for Ropivacaine hydrochloride 2 mg/ml solution for infusion	Section 4.8 of SmPC
Bupivacaine Hydrochloride	SmPCforBupivacaineHydrochloride0.125%w/vSolution for Infusion	Section 4.8 of SmPC
Placement of perineural catheter	IFU Portex Epidural Minipacks, IFU for pump	Warnings sections of Instructions for use (IFU)

Reference Safety Information (RSI) on any CTR trial will be reviewed regularly according to CTR procedures.

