11.6 Management of Toxicity and Hypersensitivity Reactions

Patients are typically assessed by both the ward nursing staff and by specialist pain nurses for signs of local anaesthetic hypersensitivity or systemic toxicity. Signs/symptoms of hypersensitivity may include new rash, facial swelling, nasal congestion, shortness of breath, coughing, wheezing, vomiting and diarrhoea, dizziness, hypotension, seizure, loss of consciousness, respiratory arrest. Signs/symptoms of local anaesthetic systemic toxicity include agitation, acute delirium, dizziness, drowsiness, tinnitus, perioral hypoaesthesia, metallic taste, dysarthria, seizures, arrhythmia, hypotension, respiratory arrest, cardiac arrest.

If local anaesthetic hypersensitivity or systemic toxicity is suspected, the infusion must be stopped immediately, and the on-call anaesthetic team contacted. If the participant is in cardiac arrest, cardiopulmonary resuscitation must commence. Alternatively, if the participant has a cardiac output, 100% oxygen should be administered, and the airway secured, as necessary. IV access needs to be confirmed or established. Seizures should be addressed quickly, and treatment options include propofol. Cardiovascular system effects, such as arrhythmias, conduction block, and progressive hypotension and bradycardia, should be managed by conventional Advanced Life Support protocols.

Local anaesthetic toxicity would be considered a SAR and would be reported within 24 hours (see Section 13 on Pharmacovigilance).

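### Table 6 lists catheter and infusion events as expected for surgery, while Table 7 gives the catheter its own reference document, and no rule says which list prevails

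*Protocol*

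**What the plan says.** Section 13.4 opens with a general rule: "The expectedness assessment should be made with reference to the current Reference Safety Information (RSI) for each IMP". Being listed in that reference is then the only test of expectedness. The section goes on to name two sets of reference information.

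- **Table 6**, headed as events expected in relation to MLLA. Of this table the text says "this should be used as the RSI when assessing the expectedness of AEs causally related to surgery". Its surgical cell contains "Retained foreign body (including unable to remove PNC", and its injury and procedural cell contains infusion related reaction and infusion site extravasation.
- **Table 7**, which gives SmPC section 4.8 for each of the three drugs. For placement of the perineural catheter it gives the warnings sections of "IFU Portex Epidural Minipacks, IFU for pump".

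Section 13.3 says causality is assessed for the drugs and for procedures. The one procedure it names is "Procedure: Placement of perineural catheter during MLLA".

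Section 13.2 makes infection at the PNC exit site and local anaesthetic toxicity SAEs in every case. It exempts grade 1 and 2 surgical complications listed in Table 6 from SAE reporting; these go on the CRF in the ordinary timeframe.

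Table 3 (section 13.1) defines a SUSAR as "A SAR, the nature and severity of which is not consistent with the Reference Safety Information (RSI) for the IMP".

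**The concern.** Table 6 describes the background of an amputation, but some of its entries come, or can come, from what the trial is testing. A catheter that cannot be removed does not occur in a patient who never had one. If such an event is read against Table 6, it is expected and surgical. If it is read against Table 7, expectedness depends on the device instructions. The protocol states both routes and ranks neither.

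The effect goes beyond a label. Table 6 also feeds the exemption in section 13.2. A low-grade PNC event that meets a seriousness criterion, for example by prolonging the hospital stay, can therefore be filed as a surgical complication instead of an SAE. Harms specific to the PNC arm would then be handled as background events of the operation both arms undergo.

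**Working it through.** There is no figure in the plan to reproduce. The check sets the passages side by side.

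**Step 1. Catheter and infusion events**

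| Event in Table 6 | Can it arise without a PNC? | Reference under Table 6 | Reference under Table 7 |
|---|---|---|---|
| Unable to remove PNC | No | Surgery list: expected | Device instructions, warnings |
| Infusion site extravasation | Yes, from other lines | Surgery list: expected | Device instructions or SmPC 4.8, if from the PNC infusion |
| Infusion related reaction | Yes, from other infusions | Surgery list: expected | SmPC 4.8 or device instructions, if from the PNC infusion |

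**Step 2. Does causality assessment choose the list?** Table 6 applies to events caused by surgery, but section 13.3 has no category for surgery as such. Its procedure is PNC placement during the amputation. An event attributed to that procedure fits both the surgery wording of Table 6 and the PNC row of Table 7. No sentence in sections 13.1 to 13.5 gives an order.

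**Step 3. Does the choice affect reporting?** Yes, through the grade 1 and 2 exemption in section 13.2, which is defined by listing in Table 6. The two always-reportable items in that section cover exit-site infection and local anaesthetic toxicity. They do not cover a retained catheter or extravasation.

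**Step 4. Drug reactions.** Section 11.6 begins its list: "Signs/symptoms of local anaesthetic systemic toxicity include agitation, acute delirium, dizziness, drowsiness, tinnitus, perioral hypoaesthesia, metallic taste, dysarthria, seizures". It continues with arrhythmia, hypotension, respiratory arrest and cardiac arrest, giving 13 signs. Each was compared with Table 6 and with section 4.8 of the levobupivacaine SmPC in Appendix 1.

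| Where listed | Signs | Count |
|---|---|---|
| Both | dizziness, seizures, hypotension | 3 |
| Table 6 only | agitation, delirium, tinnitus, dysarthria | 4 |
| SmPC 4.8 only | drowsiness, perioral hypoaesthesia, arrhythmia, respiratory arrest, cardiac arrest | 5 |
| Neither | metallic taste | 1 |

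Total: 3 + 4 + 5 + 1 = 13. Table 6 holds 3 + 4 = 7 and SmPC 4.8 holds 3 + 5 = 8. Drowsiness was matched to somnolence and seizures to convulsion. Arrhythmia was not counted for Table 6, which names only sinus bradycardia and sinus tachycardia.

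An assessor who wrongly took Table 6 for a levobupivacaine reaction would call four signs expected that SmPC 4.8 does not list.

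**Step 5. Number exposed.** With 650 participants allocated 1:1, about 650 / 2 = 325 are allocated to a PNC. This is the group in which the catheter ambiguity can arise. The four-sign difference concerns only those given levobupivacaine. That number is unknown, because section 11.4 leaves the drug to the clinical team.

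**The case against.** A reader might infer that the same serious drug reaction is a SUSAR under one table and not under the other. The text does not support this. Table 6 is limited to events caused by surgery. The opening rule of 13.4 and the SUSAR definition in Table 3 both point to the reference information for the drug, which Table 7 identifies as SmPC 4.8. Mixed causation does not reopen the question: in Table 5 a possible relationship counts as related even when other factors may have contributed, and the investigator's causality judgement cannot be downgraded. Such an event stays a SAR with one governing list. Using Table 6 for it would breach the protocol.

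Nor does the stuck catheter carry a SUSAR consequence. SAR and SUSAR are defined by relation to the drug, and a purely mechanical retention is a procedure event.

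A reader might also see a conflict with the sentence "Expectedness is not related to what is an anticipated event within a particular disease". That sentence concerns the disease, whereas Table 6 lists events of an operation, so it does not decide the matter.

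It is also fair to say that many Table 6 terms can follow surgery without any PNC, and that safeguards exist. Recognised toxicity is reported within 24 hours at any grade. Fatal or life-threatening SARs are unexpected unless the reference information explicitly says otherwise. All SARs are listed in annual reports, and the IDMC reviews safety data.

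All of this stands for drug-attributed reactions. None of it settles which list governs a PNC event, or keeps a low-grade PNC event out of the surgical exemption.

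**Conclusion.** The point holds for the catheter and its infusion. Three Table 6 entries (inability to remove the PNC without qualification, the other two when they come from the PNC infusion) fall under two stated reference lists with no precedence. The same entries can pass through the grade 1 and 2 exemption as surgical complications.

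For drug reactions the rule is already clear, and the remaining problem is the risk of misapplication. It concerns four of 13 toxicity signs and is shown for levobupivacaine only.

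Limits: the ropivacaine and bupivacaine SmPC texts and the device instructions are not shown, so no difference in content can be demonstrated for them. The general disorders cell of Table 6 is empty in the text available. The documents give no frequency for these events, so the number of reports affected cannot be estimated. The primary analysis is not touched. This is a safety-reporting defect that should be corrected.

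**What to change.** Amend sections 13.2 and 13.4 and Table 6:

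1. State in 13.4 that any event at least possibly related to a study drug or to the PNC is assessed for expectedness against Table 7 only, even if surgery is also a possible cause.
2. Limit Table 6, and the section 13.2 exemption that relies on it, to events judged related to the amputation alone.
3. Take inability to remove the PNC out of Table 6, and word the two infusion entries so that they exclude the PNC infusion.

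The toxicity signs can stay in Table 6 as possible events of surgery, because the first change prevents their use for drug-attributed reactions. The cost is a wording amendment and a briefing to sites. The downside is that a few more events may be reported as SAEs or SUSARs.
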